### **8.6 Final Study Visit**

A final study visit will be performed for all participants who began study treatment, regardless of whether or not they entered or completed the 24 week treatment course. The final visit will include:

- Final physical exam
- Blood draw
- Spirometry
- Pregnancy test (females only)

Participants recording only mild or no symptoms at the last office visit will be discharged from the study. Participants recording moderate or severe symptoms at the last office visit will require follow-up as described in 12, Safety Monitoring and Reporting.

### **8.7 Early Termination Visit**

Participants may withdraw or be dropped from the study during or between study visits, according to the criteria in Section 11.2, Participant Stopping Rules and Withdrawal Criteria. For participants who withdraw or are dropped during a study visit, the visit will be terminated. The study clinician will perform a final clinical assessment, including blood collection and a targeted physical exam, as described in Section 8.6.

Participants who withdraw or are dropped from the study between visits will be contacted by phone and will be invited to the study center for a final assessment as described in Section 8.6 above. For participants who refuse to come to the clinic, the final clinical assessment as described above may be conducted over the phone. Besides this visit, no further follow-up will be made, except for participants who are discontinued due to pregnancy or SAEs. These participants will be contacted to determine the outcome of the pregnancy or the SAE. Refer to Section 12.6, Pregnancy Reporting, for more information on AE reporting for pregnancy.

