### **8.8 Pregnancy Visit**

Females who become pregnant during the study will be discontinued immediately and no further study procedures will be performed. These participants will be followed to determine the outcome of the pregnancy; otherwise no further follow-up will be made.

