## **11 Criteria for Participant and Study Completion and Premature Study Termination**

### **11.1 Participant Completion**

The participants are considered to have completed the study once they have completed the Final Study Visit.

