**12.4 Collection and Recording of Adverse Events**

Adverse events (including SAEs) will be collected from the time of consent until a subject completes study participation or until 30 days after he/she prematurely withdraws (without withdrawing consent) or is withdrawn from the study.

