#### **12.4.2 Recording Adverse Events**

Throughout the study, the investigator at the site will record adverse events and serious adverse events as described previously (Section 12.2, Definitions) on the appropriate AE/SAE eCRF regardless of the relationship to study procedure.

Once recorded, an AE/SAE will be followed until it resolves with or without sequelae, or until the end of study participation, or until 30 days after the subject prematurely withdraws (without withdrawing consent)/or is withdrawn from the study, whichever occurs first.

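### After early withdrawal, Sections 8.7, 8.8 and 11.4/6.5 end follow-up, while Sections 12.4 and 12.4.2 collect and follow adverse events for 30 more days

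*Combined protocol and SAP*

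**What the plan says.** **Sections that end follow-up.** Section 8.7 calls for a final assessment, by phone if the participant declines to come in. It then says: "Besides this visit, no further follow-up will be made, except for participants who are discontinued due to pregnancy or SAEs". Contact under that exception serves only to learn how the pregnancy or the SAE ended. Section 8.8, for participants who become pregnant, says: "These participants will be followed to determine the outcome of the pregnancy; otherwise no further follow-up will be made". Section 11.4, which is the section on follow-up after early withdrawal, refers to Section 6.5, and the only post-discontinuation data collection there is a final blood sample.

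**Sections that continue it.** Section 12.4 collects AEs, SAEs included, from consent until participation is completed or, for those who leave early, "until 30 days after he/she prematurely withdraws (without withdrawing consent) or is withdrawn from the study". Section 12.4.2 adds: "Once recorded, an AE/SAE will be followed until it resolves with or without sequelae". Its other two end points are the end of participation and 30 days after the participant leaves early or "is withdrawn from the study, whichever occurs first".

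**A partial bridge.** In Section 8.6, "A final study visit will be performed for all participants who began study treatment", whether or not they completed the course. Moderate or severe symptoms at the last office visit are sent to Section 12 for follow-up. For the rest: "Participants recording only mild or no symptoms at the last office visit will be discharged from the study".

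**Analysis.** The primary endpoint (13.2.1) counts reported AEs and SAEs. The safety population (13.4.1) is everyone given the first injection. Section 13.4.2 describes a rate of related events during treatment, plus a tabulation of AEs and SAEs for which it states no time limit.

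**The concern.** In a safety pilot, the length of AE collection is part of the definition of the primary endpoint. For a participant who leaves early without withdrawing consent, one set of sections closes the record at the final assessment and another keeps it open to day 30.

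Staff who work from the visit procedures in Section 8 would stop. Staff who work from Section 12 would go on. The loss falls on withdrawn participants, some of whom may have stopped because they could not tolerate the injections (Section 11.2, item 3). They remain in the safety population even if they are replaced under Section 11.3.

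Two further points depend on the same window. Section 12.2.4 requires a death to be reported if the investigator learns of it in the follow-up period that the protocol defines, and the sections above define that period differently. Section 13.4.2 does not say whether an event after withdrawal belongs in the rate during treatment.

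**Working it through.** The plan gives no calculated figure on this point. The check is a comparison of the rules, followed by one subtraction.

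**1. What each section requires after the final assessment, consent not withdrawn**

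| Situation | 8.7, 8.8, 11.4/6.5 | 8.6 | 12.4 and 12.4.2 |
|---|---|---|---|
| Moderate or severe symptoms at the last office visit | No follow-up, unless an SAE caused discontinuation | Follow-up under Section 12 | Followed to resolution or day 30 |
| Unresolved mild event | No follow-up | Discharged | Followed to resolution or day 30 |
| New event after the assessment | No follow-up | Not addressed | Collected to day 30 |
| SAE or pregnancy that caused discontinuation | Contact for its outcome only | Only if symptoms are moderate or severe | All AEs to day 30; 12.6 also monitors a pregnancy to its conclusion |

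In the first row, 8.6 resolves the conflict by pointing to Section 12. In the second and third rows nothing resolves it. In the fourth, the outcome of the named event is covered, but other AEs in the 30 days are not.

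**2. Can both sets of rules be met together?** For a new event, partly. Section 12.4.1 accepts unsolicited complaints, so a site could make no contact and still record what it is told. For a recorded mild event that has not resolved, no. Section 12.4.2 requires it to be followed, and 8.7 rules follow-up out.

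**3. Length of the gap.** Let d be the number of days from withdrawal to the final assessment. The 30 days are from Section 12.4; the documents do not give d.

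Gap per withdrawn participant = max(0, 30 − d) days.

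- d = 0 (withdrawn during a visit): 30 − 0 = 30 days.
- d = 14 (assumed, one maintenance interval): 30 − 14 = 16 days.
- d ≥ 30: 0 days.

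The range is 0 to 30 days per withdrawn participant. The documents give no expected number of withdrawals, so no total for the trial is offered.

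**The case against.** **The sections are compatible.** Section 12.4 sets a window but no day-30 visit or call, 12.4.1 allows passive discovery, and 12.1 presents Section 12 as the place where safety data collection is defined. This stands in part: new events that a participant volunteers would be captured under either rule. It does not dispose of the point, because 12.4.2 requires active follow-up of recorded events and 12.1 does not say that Section 12 overrides 8.7.

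**The effect on the endpoint is slight.** No injections follow withdrawal. Section 5.1 expects the main reaction within 30 minutes of an injection, and 8.4 requires at least 30 minutes of observation. The trial has one arm and descriptive tabulations, and Section 13.6 says that its size does not allow a definitive safety assessment. A participant who shows grade 2 or 3 anaphylaxis at the last office visit is routed to Section 12 by 8.6. All of this stands, and it is why the point is minor.

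**Stronger readings that the documents do not support**

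- A reader might infer that pregnant participants are dropped. Section 12.6 continues monitoring to the end of the pregnancy. Section 8.8 names no termination visit; it only limits what is followed.
- A reader might infer that the final visit closes the AE window for everyone, because Section 11.1 says: "The participants are considered to have completed the study once they have completed the Final Study Visit". That is strained, since 12.4 lists completion and early withdrawal as separate cases and gives the second its own 30 days.
- A reader might add Section 8.4, which asks for information on delayed reactions in everyone given the first dose. It states no duration, so the final assessment can satisfy it.

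**Conclusion.** The inconsistency is real and in current text. For participants who leave early without withdrawing consent, 8.7, 8.8 and 11.4/6.5 cannot be fully reconciled with 12.4 and 12.4.2, and no rule of precedence is given. The text is wrong as written, and the severity is minor.

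What is exposed is narrow: mild events unresolved at the final assessment, and later events that are not volunteered, which could include an SAE. The size is at most 30 days of AE ascertainment per withdrawn participant, falling to none if the final assessment comes 30 or more days after withdrawal. The 16-day figure assumes a 14-day delay. Those who withdraw consent are outside the window, and those lost to follow-up cannot be contacted under either rule.

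The point does not depend on whether there is one site or several, because a single site would also have to choose between the sections. A reader might infer that the primary safety result is materially biased. The documents do not support that: there is no comparison arm, and neither the number of withdrawals nor the timing of the final assessment is given.

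**What to change.** 1. Amend 8.7, 8.8 and 11.4/6.5 so that AE collection and follow-up after withdrawal match the 30-day window already stated in 12.4, for participants who have not withdrawn consent. Contact by phone is enough; 8.7 already accepts it for the final assessment. Align the discharge sentence in 8.6 for participants who leave early.
2. In 12.2.4, name that window as the follow-up period within which a death must be reported.
3. In 13.4.2, state whether events after withdrawal but inside the window count in the rate during treatment or are tabulated separately.

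The cost is wording in these sections and a few phone calls to withdrawn participants. No new visit or procedure is needed.

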### **8.8 Pregnancy Visit**

Females who become pregnant during the study will be discontinued immediately and no further study procedures will be performed. These participants will be followed to determine the outcome of the pregnancy; otherwise no further follow-up will be made.

### **8.9 Unscheduled Visits**

Study participants may attend unscheduled visits for a medical evaluation if they experience moderate to severe symptoms.

### **8.10 Visit Windows**

During dose escalation, 2 injections will be given each week separated by at least 2 days. Dose escalation may be accomplished over a maximum of 18 weeks.

Bi-weekly maintenance visits will be scheduled within the second calendar week following the previous maintenance visit. See the MOP for details regarding visit scheduling.

## **9 Mechanistic Assays**

Whole blood will be collected by venipuncture every month during the maintenance period, and will be processed according to the MOP. The blood will be tested for biomarkers of allergen immunotherapy, such as mouse-specific IgE, IgG, IgG4 antibodies, and in-vitro mouse antigen binding to B-cells (see Appendix A).

## **10 Biospecimen Storage**

Unused samples of biological specimens (blood) collected during the course of the study will be stored (described in the MOP) for future use for tests that may or may not be planned. These tests may or may not be related to the study of asthma and allergy. Participants will be asked to give permission for long-term storage and future use during the consent process. Samples may be stored indefinitely.

## **11 Criteria for Participant and Study Completion and Premature Study Termination**

### **11.1 Participant Completion**

The participants are considered to have completed the study once they have completed the Final Study Visit.

### **11.2 Participant Stopping Rules and Withdrawal Criteria**

Participants will be withdrawn from the study if the following events occur:

1. SAE related to investigational agent
2. Anaphylactic reaction grade 2 or 3 (see Section 12.3.2, Grading Criteria for Anaphylaxis)
3. Inability to tolerate the build up to or the MSD due to excessive discomfort/symptoms or large local reactions after a second attempt at dose escalation
4. The need to start immunotherapy or any chronic immunosuppressive medications (e.g., greater than 2 courses of oral or parenteral corticosteroids)
5. Require a dose of greater than 500 mcg of fluticasone per day or the equivalent of another inhaled corticosteroid to maintain asthma control
6. Development of any serious medical illness whose natural history, sequela, or treatment would be worsened or impaired by continuation in the protocol
7. The study treatment is no longer in the best interest of the participant
8. Participant is “lost to follow-up,” as defined in the MOP
9. Pregnancy
10. A lapse in dosing of more than 3 weeks during escalation
11. Missing more than 2 consecutive treatment visits during maintenance
12. Missing 25% or more of all maintenance visits (miss more than 2 maintenance visits)

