## 3 Study Design

### 3.1 Description of Study Design

This study is an open label multi-site trial of mouse allergenic extract administered by subcutaneous injection in approximately 10 - 12 adults ages 18 to 55 years with asthma. The study will be based on a continuous treatment schedule with mouse allergenic extract for a period of approximately 24 weeks. It is primarily designed to study the safety of this therapy.

There will be a Screening Visit followed by a Dose Initiation Visit, at which the subject will receive their first injection. Up to 2 doses of SCIT will be given weekly during dose escalation, separated by a minimum of 2 days. Dose escalation will occur over a minimum of 11 weeks. Dose escalation can be delayed at any point if there are excessive large local reactions or other concerns, although to continue on to maintenance each subject will need to reach the maintenance dose in a maximum of 18 weeks. Once the maintenance dose is achieved, bi-weekly visits will continue to complete a total of 24 weeks of treatment.

Blood will be collected at baseline and then monthly for assessment of biomarkers of allergen immunotherapy, including mouse specific IgE, IgG, IgG4, and inhibition of mouse antigen binding to B-cells. Mouse skin testing will be performed at screening. (See Visit Activities Summary, Appendix A)

Adverse events (AEs) will be assessed at each study visit. Allergy and asthma symptom questionnaires will also be administered throughout the study.

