**Table 8.5.1 Dose Escalation**

Dose #	Week* #	Concentration	Volume	Approximate Dose	Mus m 1
1	1	1:10,000	0.05 ml		
2	1	1:10,000	0.10 ml		
3	2	1:10,000	0.20 ml		
4	2	1:10,000	0.40 ml		
5	3	1:1,000	0.05 ml		
6	3	1:1,000	0.10 ml		
7	4	1:1,000	0.20 ml		
8	4	1:1,000	0.40 ml		
9	5	1:100	0.05 ml		
10	5	1:100	0.10 ml		
11	6	1:100	0.20 ml		
12	6	1:100	0.40 ml		
13	7	1:10	0.05 ml		
14	7	1:10	0.10 ml		
15	8	1:10	0.20 ml		
16	8	1:10	0.40 ml		
17	9	1:1	0.05 ml		
18	9	1:1	0.10 ml		
19	10	1:1	0.15 ml		
20	10	1:1	0.20 ml		
21	11**	1:1	0.30 ml		
22	11	1:1	0.40 ml		
Maint.***	12-24	1:1	0.40 ml		6.2 mcg

\* During dose escalation, 2 injections will be given each week separated by at least 2 days

\*\* Dose escalation may be accomplished over a maximum of 18 weeks

\*\*\* During maintenance, doses will be given every 2 weeks

For the first 11 weeks of the 24-week treatment course participants will receive two injections per week, separated by at least 2 days, at the escalating doses as described in Table 8.5.1. Dose escalation can be delayed at any point if there are excessive large local reactions or other concerns, although to continue on to maintenance each subject will need to reach the maximum study dose in a maximum of 18 weeks. A clinician and appropriate emergency supplies will be readily available to treat any adverse reactions. Participants will be discharged after the 30 minute waiting period if they show no signs or symptoms greater than mild, as defined in Section 12.3.1, or at the discretion of the study clinician.

Dose escalation will continue according to the schedule unless there are lapses in dosing or reactions occur. Dosing will be modified as follows for lapses in dosing or reactions:

- For a lapse in dosing of more than two weeks during escalation, the dose from the previous visit will be repeated.
- For a lapse in dosing of more than three weeks during escalation, the subject will be discontinued from the protocol.
- For one missed dosing visit while on maintenance, the maintenance dose will be continued.
- For two missed maintenance doses while on maintenance, the dose will be reduced by 50% and re-escalated the following week.
- For more than two consecutive missed dosing visits while on maintenance, the subject will be discontinued from the protocol.
- For local reactions 6-11 cm in diameter, the dose will be repeated.

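### Withdrawal criterion 12 in section 11.2 states one mandatory threshold in two forms that disagree: with 6 or 7 maintenance visits, the percentage is met at two missed visits and the count only at three

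*Combined protocol and SAP*

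**What the plan says.** Section 11.2 lists events after which participants are to be withdrawn; the wording is mandatory. Two items concern missed maintenance visits:

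- Item 11, a consecutive rule: "Missing more than 2 consecutive treatment visits during maintenance".
- Item 12, a cumulative rule: "Missing 25% or more of all maintenance visits (miss more than 2 maintenance visits"). The count in parentheses restates the percentage before it.

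The missed-dose bullets in section 8.5.1 also cover maintenance:

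- one miss: "For one missed dosing visit while on maintenance, the maintenance dose will be continued";
- two misses: "For two missed maintenance doses while on maintenance, the dose will be reduced by 50% and re-escalated the following week", without saying whether the two must be consecutive;
- more than two in a row: "For more than two consecutive missed dosing visits while on maintenance, the subject will be discontinued from the protocol".

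The number of maintenance visits follows from the schedule. Section 3.1 says "Dose escalation will occur over a minimum of 11 weeks" and "Once the maintenance dose is achieved, bi-weekly visits will continue to complete a total of 24 weeks of treatment". The footnote to Table 8.5.1 says "During maintenance, doses will be given every 2 weeks". Sections 3.1, 8.5.1 and 8.10 allow escalation to run to 18 weeks, and the 24-week total is not extended.

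**The concern.** A threshold given as a percentage with a count in parentheses should yield the same decision either way. Here the visit total is small enough for one visit to change the answer. A participant with exactly two missed maintenance visits must be withdrawn under one half of item 12 and not under the other, and the protocol does not say which half governs. Sites could therefore treat the same attendance record differently, and either choice could be called a deviation from the other half of the line.

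At stake are the rest of that participant's maintenance injections (up to 6 − 2 = 4 on a six-visit schedule, if the first two are the ones missed) and the monthly maintenance blood samples for the biomarkers (section 9). Replacement may also be affected. Section 11.3 says withdrawn participants are replaced, whereas section 6.5 rules this out for those who stop after the early injections. With about 10 participants, each one is roughly a tenth of the data.

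**Working it through.** **Inputs.** From Table 8.5.1: 22 escalation injections in weeks 1 to 11, then one injection every 2 weeks in weeks 12 to 24. From section 13.6: about 28 injections per participant, 280 in all for 10 participants.

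**Reproducing the plan's own figure.**

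- First maintenance visit in week 13: weeks 13, 15, 17, 19, 21, 23 = 6 visits; 22 + 6 = 28 injections, as in section 13.6.
- First maintenance visit in week 12: weeks 12, 14, …, 24 = 7 visits; 22 + 7 = 29, still about 28.

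The standard schedule therefore has V = 6 or 7 maintenance visits.

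**Where each form is met.** The percentage form needs the smallest k with k/V ≥ 0.25. The count form needs k = 3.

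| V | 1 miss | 2 misses | 3 misses | Percentage form met at | Count form met at |
|---|---|---|---|---|---|
| 6 | 16.7% | 33.3% | 50.0% | 2 | 3 |
| 7 | 14.3% | 28.6% | 42.9% | 2 | 3 |

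**Could another visit total reconcile them?** For the forms to agree, 2/V must be below 0.25 and 3/V at least 0.25, so V must be 9 to 12. Nine two-weekly visits span 1 + 8 × 2 = 17 weeks, but only 24 − 11 = 13 are available. Counting the final visit as a maintenance visit gives V = 7 or 8, and 2/8 = 25.0% still meets the percentage form.

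**Against section 8.5.1.** The two-missed-dose bullet continues treatment at a modified dose. This is compatible with the count form. It conflicts with the percentage form whether or not the two misses are consecutive, because two misses are already at least 2/7 = 28.6%.

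**Longer escalation.** Let the first maintenance visit fall one or two weeks after the last escalation week, with visits every 2 weeks up to week 24:

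| Last escalation week | 11 | 12 | 13 | 14 | 15 | 16 | 17 | 18 |
|---|---|---|---|---|---|---|---|---|
| Maintenance visits left | 6–7 | 6 | 5–6 | 5 | 4–5 | 4 | 3–4 | 3 |

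If the denominator is the participant's own visits, one miss is 1/4 = 25.0% or 1/3 = 33.3% once escalation ends in weeks 16 to 18. The percentage form is then met at a single miss, while the count form still needs three. If the denominator is the standard 6 or 7, it is met at two. The protocol does not say which denominator is meant.

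**How often exactly two misses would occur.** The documents give no missed-visit rate, so the per-visit rates p below are assumptions, with misses taken as independent. P(exactly 2) = C(V,2) p² (1 − p)^(V−2), with C(6,2) = 15 and C(7,2) = 21.

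| p | V = 6 | V = 7 |
|---|---|---|
| 5% | 3.1% | 4.1% |
| 10% | 9.8% | 12.4% |
| 20% | 24.6% | 27.5% |

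Exactly two is the relevant event for a lasting disagreement, because at three misses both forms require withdrawal.

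**The case against.** The strongest reply is that sites will read the parenthesis as the operative rule, since it is concrete and fits the section 8.5.1 bullet for two missed doses. That is a plausible reading, but nothing in the protocol says the parenthesis governs. If it does, the percentage beside it is wrong for this schedule.

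A second reply is that visit-scheduling details are left to the manual of procedures (section 8.10), which may define the denominator. It may. Item 12 does not refer to the manual, although item 8 does for loss to follow-up, and the two forms conflict at V = 6 and V = 7 whatever the manual says about long escalations. The single-miss result is weaker, since it holds only if the denominator is the participant's own shortened schedule.

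A third reply is that little depends on this. The safety population is everyone who receives the first injection (section 13.4.1), a final blood sample is drawn on discontinuation (section 6.5), and the biomarker analyses are descriptive (section 13.4.3). This stands, and it limits the importance of the point.

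A reader might go further and infer that neither form of item 12 agrees with section 8.5.1, because three scattered misses lead to withdrawal under item 12 but not to discontinuation under the 8.5.1 bullets. The documents do not support that. Section 8.5.1 does not present itself as the full list of reasons to stop, and section 11.2 gives many others. Item 11 is already the consecutive rule, so a cumulative item 12 can properly add to it. Only the percentage form conflicts with the two-missed-dose bullet.

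**Conclusion.** The contradiction is real, and on the standard schedule it needs no assumption beyond the protocol's own visit spacing: the two halves of item 12 give opposite answers for a participant with exactly two missed maintenance visits out of 6 or 7. How many participants this would affect is not known from the documents. The illustrative range of 3.1% to 27.5% per participant depends on the assumed miss rates, on independence and on an 11-week escalation. The claim that one miss can be enough after a long escalation is conditional on an undefined denominator.

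This is an ambiguity in a mandatory conduct rule, with modest consequences for exposure and biomarker sampling and a possible effect on replacement. It does not threaten the primary safety analysis: nobody leaves the safety population under either form, and no power or error-rate calculation depends on item 12.

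**What to change.** Reword section 11.2 item 12 so that the percentage and the count give the same decision on the planned schedule, or keep only one of them. Reconcile the result with the two-missed-dose bullet in section 8.5.1. State what counts as all maintenance visits, in particular for participants whose escalation runs beyond 11 weeks, and whether the final visit is included. Which threshold applies, and in which form, is a decision for the sponsor's clinicians.

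The cost is a wording change in two sections, with no change to data collection or analysis.
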